Research question WP 4.1 - What services are delivered by NHS DPP and what is the extent of participation in the NHS DPP intervention?

Research question WP 4.2 - How does service delivery and participation in the programme vary by (a) the 4 NHS DPP providers (and any variation within provider by area) and the associated variation in content and delivery (b) between patient subgroups?

Research question WP 4.3 – What are the outcomes of patients in the NHS DPP intervention, including wellbeing score, weight change, HbA1c, and mortality?

Research question WP 4.4 – How do outcomes vary by (a) the 4 NHS DPP providers (and any variation within provider by area) and the associated variation in content and delivery (using data from work package 3) (b) between patient subgroups?

Methods: All research questions will be addressed using a minimum individual patient data set. NHS DPP have already stipulated that NHS DPP providers will be required to collect and supply this data, which will then be passed in anonymised form to the research team. The individual dataset will include 48 items, including referrer, delivery organisation, personal/demographic details, process data (including records of each session) and outcome data (Warwick-Edinburgh Mental Wellbeing Scale, weight change, and HbA1c).

Based on the NHS DPP announcement that it expects to provide 100,000 places per year by 2020 (https://www.england.nhs.uk/ourwork/qual-clin-lead/diabetes-prevention), we have made the assumption that there will be 50,000 individuals in 2017/18; 80,000 in 2018/19 and 100,000 in 2019/20, a total of 230,000 individuals.

We will match this individual patient data to service-level data on what is being provided by the providers in different areas, collected by the 'Implementation' and 'Service and Fidelity' work packages. This will be a rich individual level longitudinal dataset, that will allow patients be followed over time, through the steps of invitation, baseline assessment, enrolment, service delivery, completion, and end-of-service outcomes.

We anticipate that, like any administrative dataset, there will be error and missing data. As with other aspects of the evaluation, the DIPLOMA team will work closely with the NHS DPP to ensure that suitable processes are in place to ensure data collection is as accurate and complete as possible. We will provide feedback on missing data through our initial analyses, and follow up with providers if problems continue.

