We will use descriptive statistics to assess overall outcomes, and multivariable regression methods to estimate the relationship between patient, provider and service characteristics and participation (question 4.2) or outcomes (question 4.4). For analysis, we will use multilevel modelling of individual characteristics (focusing on health inequalities – WP1) and service delivery (number of sessions attended; area/provider; and important elements of service delivery identified in WP3 (e.g. behaviour change techniques) on the outcomes collected by NDPP providers (weight, HbA1c, WEMWBs etc.). We will work closely with providers to minimise missing data, and we will report the extent of missing data. We will consider multiple imputation methods, if we assess that the data meets the assumption of NMAR.

WP4 will use the insights/models developed in the WP1-3 to influence the choice of variables in our statistical models: on health inequalities (WP1) and service delivery/fidelity (WP3). We will incorporate these to estimate their effect on participation, service delivery and outcomes for NDPP attenders.

We will produce regular reports to inform ongoing NHS DPP service delivery, drawing on exemplars such as the IAPT dataset.⁸⁷ To ensure the relevance of these reports, a detailed analysis plan will be written in advance, in negotiation with the NHS DPP, and this can be re-negotiated over the course of the project.

Timing of analysis: Analysis will be undertaken at three time points: Summer 2018 (using year 1 data, around 50,000 patients); summer 2019 (using Year 1 and 2 data, around 130,000 patients), summer 2020 (using complete dataset, around 230,000 patients). The earlier reports will focus on reporting who is invited to attend, baseline measures and enrolment, but as time progresses, we will be able to say more about the services delivered, completion rates and end-of-service outcomes.

Amendment to WP4

Non-substantial amendment

WP 4.5 Comparison of face to face and digital DPP – observational cohort study, secondary analysis

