These two anonymised datasets are supplied to us by NHS England, collected from patients participating in the NHS DPP (individual characteristics, referral source, extent of participation in the DPP, and health outcomes). No personal details will be available to the research team. We already have the first dataset (face-to-face MDS, as used in the previous WP4 analysis) and NHSE have agreed to provide us with the second dataset (digital DPP). The second dataset contains similar variables, but on a different population. We are signing a Memorandum of Understanding with NHSE to cover the data sharing and we will follow the same UoM information governance procedures as our current DIPLOMA analyses.

Power calculation

HbA1c at 6 months among those taking the F2F DPP is 39.9 mmol/ml (SD 4.08). A reduction in HbA1c of 5 mmol/ml (0.5%) or more is considered to be clinically important so if the difference in the means of the two groups is less than 5 they can be regarded as having a similar effect. Assuming a standard deviation in both F2F and digital DPP of 4.08, 90% power, alpha 5% and 5-to-1 allocation of controls to cases, to observe a difference of 2 mmol/ml we would need a total of 486 people (81 digital, 405 F2F). There are 2200 digital participants with 6 month outcomes, which should provide sufficient numbers, after matching.

Missing data

Multiple imputation by fully conditional specification will be used to reduce bias due to missingness (up to 30% among covariate values in the F2F MDS).24, 25 Multiple imputation has already been applied to the F2F dataset, and a similar approach will be implemented in the digital dataset.

The analysis of clinical effectiveness will focus on completers: in both datasets, outcome data was only collected on those who stayed in the programme until the outcomes were recorded, so there will be considerable, systematic bias in terms of differences between responders and non-responders.

Analysis

1. Descriptive statistics

We will describe patient participation (registrations, starts and completion) in digital and face to face, and explore differences between digital and face to face patients.

2. Differences in participation (start and completion)

We will estimate differences in participation (registration, start and completion) between digital and face to face. Differences will be explored using three approaches

- a) Raw (uncorrected) differences in participation.

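### The WP4 methods make multiple imputation conditional on the data being NMAR, which reverses the condition standard imputation needs and sits badly with WP 4.5

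*Protocol*

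**What the plan says.** Work package 4 (Outcomes) analyses the providers' minimum dataset without a comparator group. Its Methods expect incomplete data: "We anticipate that, like any administrative dataset, there will be error and missing data". The planned analyses are descriptive statistics and multilevel regression "on the outcomes collected by NDPP providers (weight, HbA1c, WEMWBs etc".). The rule for missing data is one sentence: "We will consider multiple imputation methods, if we assess that the data meets the assumption of NMAR". It does not say which variables would be imputed, and it names no model for a departure from MAR.

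WP 4.5, added later to compare face-to-face with digital delivery, has its own Missing data paragraph. It states: "Multiple imputation by fully conditional specification will be used to reduce bias due to missingness (up to 30% among covariate values in the F2F MDS"). It adds: "Multiple imputation has already been applied to the F2F dataset, and a similar approach will be implemented in the digital dataset". No NMAR condition appears there. The WP 4.5 Data section identifies the face-to-face dataset as the one used in the previous WP4 analysis. The same Missing data paragraph limits the analysis of clinical effectiveness to completers, because "outcome data was only collected on those who stayed in the programme until the outcomes were recorded", and it acknowledges that this brings systematic bias.

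WP 5.2 design 1 also plans multiple imputation if needed, again without an NMAR condition.

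**The concern.** MAR means that, given the observed data, the chance that a value is missing does not depend on the value itself. Standard multiple imputation draws missing values from a model fitted to the observed data, so it needs that assumption (or the stronger one of missing completely at random). Under NMAR the people with missing values differ from otherwise similar people in a way the observed data do not show. Imputed values then inherit the pattern of those observed, unless the analyst builds in an explicit difference such as a delta adjustment, a pattern-mixture or selection model, or reference-based imputation.

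The WP4 sentence therefore has the condition backwards for the standard method. It is also not a usable trigger, since observed data alone cannot settle whether missingness is MAR or NMAR. What is at stake is the WP4 description of weight, HbA1c and wellbeing outcomes, and how they vary by provider and patient group (research questions 4.3 and 4.4). An analysis plan that follows the sentence would inherit the error.

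**Working it through.** The protocol gives no figure to reproduce on this point. The check sets the passages side by side and then illustrates the principle.

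**Passages compared**

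| Place | Condition for imputation | Method named |
|---|---|---|
| WP4, Methods | Considered if data meet NMAR | None; no departure model |
| WP 4.5, Missing data | None stated | Fully conditional specification; already applied to the face-to-face data |
| WP 5.2, design 1 | If needed | Methods for longitudinal data |

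Only the first row carries an NMAR condition, and the second row concerns the same face-to-face data. The two WP4 statements do not describe one coherent policy.

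**Illustration of the principle**

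Input from the protocol (WP 4.5, Power calculation): "HbA1c at 6 months among those taking the F2F DPP is 39.9 mmol/ml (SD 4.08").

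Assumptions not in the protocol:
- one baseline covariate x, standardised, with correlation r = 0.3, 0.6 or 0.8 with the outcome;
- logit P(missing) = -0.98 + 1.0 × d, where d = x (MAR) or d = the standardised outcome itself (NMAR), giving about 31% missing;
- 20 replicates of n = 20,000, with 10 imputations from a normal regression of the outcome on x.

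Bias in the mean = estimate - 39.9, in HbA1c units:

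| r | MAR: complete cases | MAR: imputed | NMAR: complete cases | NMAR: imputed |
|---|---|---|---|---|
| 0.3 | -0.31 | 0.01 | -1.05 | -0.97 |
| 0.6 | -0.64 | -0.01 | -1.05 | -0.70 |
| 0.8 | -0.85 | 0.00 | -1.06 | -0.42 |

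Under MAR, imputation removes essentially all the bias. Under NMAR the share removed is 1 - (imputed bias / complete-case bias):
- r = 0.3: 1 - 0.97/1.05 = 8%
- r = 0.6: 1 - 0.70/1.05 = 33%
- r = 0.8: 1 - 0.42/1.06 = 60%

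The table shows direction only; the sizes follow from the assumptions. It concerns an overall mean. In a regression where only the outcome is missing and everything that predicts missingness is already a covariate, complete cases are also valid under MAR. Imputation then gains mainly from missing covariates and from predictors outside the model.

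**Can a size be derived?** No. The protocol gives no outcome-missingness rate for the main WP4 dataset. The nearest counts are for the digital pilot in WP 4.5: 4409 registered and 2687 gave outcome data, so (4409 - 2687)/4409 = 39% did not. Those are registrations on a different programme and may include people who never started. Nothing states how the outcomes of leavers differ from those of stayers.

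**The case against.** The strongest reply is that NMAR is a slip for MAR. WP 4.5 shows the team imputing the same face-to-face data by an ordinary MAR method, and the WP4 sentence promises only to consider imputation. That is probably right, and nothing shows that the NMAR condition governed any analysis. It does not rescue the text: the hedge is about whether to impute, and the condition attached is still wrong.

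A second reply is that imputation can be done under NMAR. It can, with an explicit model, but none is named. A third is that WP4 promises a detailed analysis plan for its reports. Leaving imputation details to such a plan would be no fault, but this is a condition stated wrongly, not a detail left out.

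Three stronger readings are tempting, and the document does not support them.

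- **Dropouts would be shown doing as well as stayers.** The WP4 sentence does not say that outcomes would be imputed. Where the protocol is specific, in WP 4.5, the missingness it quantifies is in covariates, and the clinical analysis is confined to completers with the bias acknowledged.
- **A large percentage overstatement of weight loss.** Any such figure needs assumed dropout rates and assumed losses. It would also measure informative dropout in general. Complete-case analysis, or MAR imputation whose predictors do not explain the leavers' results, would give the same answer. In the illustration, imputing under NMAR was no worse than using complete cases.
- **Corrupted cost-effectiveness inputs.** WP 7.2 does take average quality-of-life gains among participants from WP4. The effectiveness input to the decision model in WP 7.4, the numbers developing diabetes, comes from the National Diabetes Audit and not from WP4 weight or HbA1c.

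**Conclusion.** The point holds as an error in a stated analysis rule. The WP4 condition is the reverse of what standard multiple imputation requires, no departure model is supplied, and the sentence is out of line with WP 4.5. The practical cost, if it were followed literally, is twofold: bias left in place when data are NMAR, and no stated basis for imputing when data are MAR and imputation would help.

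This conclusion rests on reading multiple imputation as the standard method, which the fully conditional specification in WP 4.5 supports. No size can be put on the bias from the protocol.

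The sentence should be fixed, but it does not threaten the main findings. WP4 is a within-programme analysis, the comparative analysis is assigned to WP5, and the main WP 5.2 outcome, conversion to diabetes, does not depend on this sentence.

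**What to change.** Replace the WP4 sentence with a rule consistent with WP 4.5: multiple imputation under MAR, with an imputation model that conditions on baseline values, provider and attendance. According to the WP4 Methods, the minimum dataset already holds personal details, delivery organisation and session records.

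Because outcomes exist only for people who stayed, and MAR cannot be verified from the observed data, add one of two things:

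- a statement that WP4 outcome results apply to people with recorded outcomes; or
- an NMAR sensitivity analysis for outcomes after dropout, either delta-adjusted or reference-based, with its assumptions stated.

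The cost is one or two sentences of text and, under the second option, a little more analysis on data already held. No new data collection is needed.

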Rationale: The DIPLOMA project has been awarded additional funding to compare the face-to-face and digital delivery of the NHS Diabetes Prevention Programme (DPP), in terms of population characteristics, participation rates and health outcomes. Face-to-face and pilot digital DPP offered similar content with different delivery methods. The delivery of these two programmes at the same time offers a unique opportunity to compare face-to-face and digital delivery. This analysis will contribute to RQs 4.2 and 4.4.

Objectives:

- 1. Compare the population characteristics of those who take up the options of face-to-face and digital delivery.
- 2. Compare participation rates between face-to-face and digital delivery.
- 3. Compare the clinical effectiveness of face to face and digital delivery, among those who complete the programme

Populations

Face to face DPP was offered to adults with NDH. Digital DPP was offered to 1) adults with NDH; 2) adults who are overweight or obese. Overall, 4409 people registered for the programme during the 12 months pilot, 3612 with NDH and 797 who were obese. Of these, 2687 people provided outcome data

- 1. Choice (32.6% of registrations). Within the Digital DPP, four areas (BNSSG, Bucks, Lancs and Salford) offered patients a choice between digital and face to face. The NHSE Minimum Data Set (MDS) is available for the f2f providers in these areas, allowing a direct comparison.
- 2. Digital only (59.7% of registrations). This was delivered in areas where there was no F2F programme, but it did not last long, because F2F was gradually rolled out to all areas.
- 3. Decliners (7.7% of registrations). Only people who declined to take up the F2F programme were offered digital.

Data

Two datasets will be combined for analysis:

- Face to face DPP dataset
- 2. Digital DPP dataset

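### WP 4.5: the primary matched comparison of face-to-face and digital delivery is not limited to people with NDH, has no overlap rule, and pools digital pathways with different access to face-to-face

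*Protocol*

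**What the plan says.** All references are to the protocol, Work package 4, Amendment to WP4, WP 4.5.

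- **Populations, eligibility.** "Face to face DPP was offered to adults with NDH". For the other mode, "Digital DPP was offered to 1) adults with NDH; 2) adults who are overweight or obese". The counts are: "4409 people registered for the programme during the 12 months pilot, 3612 with NDH and 797 who were obese". Outcomes are available for 2,687 of the registrants.
- **Populations, pathways.** Choice areas supply 32.6% of digital registrations, and these four areas are where the protocol says the two modes can be compared directly. Digital-only areas supply 59.7%: "This was delivered in areas where there was no F2F programme", a situation described as short-lived because F2F was being rolled out everywhere. Decliners supply 7.7%: "Only people who declined to take up the F2F programme were offered digital".
- **Data.** The two datasets are to be combined, and the digital one is acknowledged to cover a different population.
- **Power calculation.** The plan needs 81 digital and 405 F2F participants for a 2-unit HbA1c difference, and adds: "There are 2200 digital participants with 6 month outcomes, which should provide sufficient numbers, after matching".
- **Analysis.** The matched cohort is labelled primary. Every person receives a propensity score for mode from baseline demographic, service and administrative variables. Matching is nearest neighbour, five F2F to one digital, without replacement. Outcome models adjust for baseline scores, provider and CCG. Weight and HbA1c are to be handled in a similar way to participation.

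No sentence limits the matched set to people with NDH, sets a caliper or common-support rule, or says how the three pathways enter.

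**The concern.** Propensity matching is informative where people could have received either mode. Three parts of the digital dataset fall short of this, each for a different reason.

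- **Non-NDH users** did not meet the F2F eligibility condition, so an F2F patient with NDH is not a valid match.
- **Decliners** were offered F2F and refused. F2F participants had not refused, and the measured covariates are unlikely to capture that preference.
- **Digital-only areas** had no F2F at the time, so mode and area coincide. Provider and CCG adjustment cannot separate the two well there. A score that includes area loses overlap; a score that omits it leaves area and roll-out timing mixed with mode.

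Nearest-neighbour matching with no caliper still returns a match in all three cases. The resulting contrast in completion, weight and HbA1c would mix delivery mode with eligibility, preference and area. HbA1c is the most exposed outcome because NDH is defined by glycaemia. The WP9.3 inclusion criteria put NDH at HbA1c 42–47 or fasting glucose 5.5–6.9, so if non-NDH users lie below that range, baseline adjustment extrapolates.

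**Working it through.** **The plan's own sample size.** Inputs from the Power calculation: SD 4.08, difference 2, 90% power, alpha 5% (taken as two-sided), five F2F per digital participant.

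n(digital) = (1 + 1/5) × [4.08 × (1.960 + 1.282) / 2]² = 52.5, so 53 digital and 265 F2F.

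The stated 81 and 405 are not reproduced; they correspond to about 98% power, or to a difference of about 1.61. The stated number is larger than its inputs require, which is conservative and a separate matter. I use 81 as the hurdle below.

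**Composition of the digital registrations**

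- Non-NDH: 797 / 4,409 = 18.1%. NDH: 3,612 / 4,409 = 81.9%.
- Choice: 0.326 × 4,409 ≈ 1,437. Digital-only: 0.597 × 4,409 ≈ 2,632. Decliners: 0.077 × 4,409 ≈ 339. The shares sum to 100%.

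**Digital participants left after restriction.** The base is the 2,200 with 6-month outcomes. I assume outcome completeness is equal across eligibility types and pathways, which the protocol does not state.

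- NDH, all pathways: 2,200 × 0.819 ≈ 1,802.
- Choice areas, any eligibility: 2,200 × 0.326 ≈ 717.
- NDH in choice areas, if the NDH share is the same in every pathway: 717 × 0.819 ≈ 588.
- Bounds without that equal-share assumption: lower 717 − 2,200 × 0.181 ≈ 320 (every non-NDH user is in a choice area); upper 717 (none is).

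**Detectable difference at 90% power and 1:5**: 3.242 × 4.08 × √(1.2 / n)

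| Digital n | Detectable HbA1c difference | F2F matches needed (5n) |
|---|---|---|
| 2,200 | 0.31 | 11,000 |
| 1,802 | 0.34 | 9,010 |
| 717 | 0.54 | 3,585 |
| 588 | 0.60 | 2,940 |
| 320 | 0.81 | 1,600 |

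Each is well below the 2-unit target. The last column is a condition: the protocol gives no F2F count, overall or in the four choice areas.

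**Leverage of each group on the pooled contrast.** If matching and adjustment leave a group 1 unit away from its matches for reasons other than mode, the pooled difference shifts by that group's share: about 0.18 for non-NDH users, 0.60 for digital-only areas and 0.08 for decliners. The non-NDH and pathway shares overlap, so these do not add. The documents give neither the size nor the sign of any residual difference.

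**The case against.** Several counter-arguments carry weight.

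- **Most digital users can still be matched.** A reader might add 59.7% and 7.7% and infer that 67% of the digital group had no chance of F2F, or that most of it has no counterpart. The protocol does not support that. Decliners were offered F2F. Digital-only status was temporary. About 82% of registrants have NDH and could be matched to F2F patients in other areas, or in the same area after roll-out; matching within CCG is not required. By eligibility, only 18.1% lack a counterpart. This objection stands.
- **Pooling everyone is inferred.** The protocol never says outright that all three pathways are matched together, and it allows for loss through matching. The 2,200 might already be limited to NDH: 2,687 × 3,612 / 4,409 ≈ 2,201. The protocol does not say so, and that closeness may be chance. If it were so, the equal-share NDH choice-area figure would be about 717, and the conclusion on numbers would be unchanged.
- **Calipers can be left to an analysis plan.** True of the detail. But the protocol itself fixes the primary method, the people scored, the ratio and the number available, and these do not fit its own description of the populations.
- **Choice areas are not bias-free.** Patients there select their own mode. Digital-only areas remove that individual choice at the price of area differences. Which bias matters more is a judgement, so making choice areas the sole primary analysis is not required by the document.
- **Baseline adjustment helps.** It does where baseline ranges overlap; that is not assured for non-NDH users.

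**Conclusion.** The point holds in a limited form. Followed as written, WP 4.5 allows F2F-ineligible people (18.1% of digital registrants) into the primary matched comparison with NDH patients. It also pools choice areas, digital-only areas and decliners without an overlap rule, although the protocol identifies the four choice areas as its direct comparison. The comparison of modes can then be biased, HbA1c most of all, by an amount and in a direction the documents do not determine.

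For the non-NDH users the problem is one of validity. For decliners and digital-only areas it is residual confounding that should be made visible; it does not show that matching is impossible there.

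Restriction is affordable. About 1,800 digital participants with NDH, or about 590 (range about 320 to 717) with NDH in choice areas, compare with the 81 required. These counts are illustrative. They rest on equal outcome completeness, the 590 also on an equal NDH share across pathways, and the power on enough F2F matches being available.

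**What to change.** In WP 4.5, for both participation and clinical outcomes:

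1. Limit the matched analysis to people with NDH in both datasets, and describe non-NDH digital users without matching them.
2. Add a common-support or caliper rule and report how many people it removes.
3. Report the matched result separately for choice areas, digital-only areas and decliners.
4. State whether the primary estimate uses choice areas alone or all NDH pathways, with the reason, acknowledging that self-selection is traded against area differences.
5. Replace the 2,200 with the actual number with NDH and 6-month outcomes, and the number of those in choice areas, once known. Give the F2F numbers available for matching alongside. The illustrative counts above should not be written into the protocol.

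The change is to wording and analysis code and uses data already planned. It costs a smaller digital group and a result that applies to a narrower population.

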Overview of methods: Work package 1 will use a combination of quantitative analysis of existing data sources, and qualitative research. The first research question will use data from the NHS DPP and existing administrative data sources to explore access. Research question 4 will explore if access is influenced by the understandings and experiences of participants.

When the initial research proposal was written, the National Diabetes Audit data was not considered useful, as at that point in time it did not contain data on non-diabetic hyperglycaemia. This information has since been added to the National Diabetes Audit. The National Diabetes Audit offers a more complete coverage of general practice than CPRD data, and so will now replace the CPRD analysis which was originally planned (conditional on checks of completeness and quality of the NDA).

Research question WP 1.1: Are there inequalities in the identification of patients eligible for the NHS DPP? Is there an under-representation of participants with protected characteristics in general practice compared to the general population of adults at risk of diabetes?

Methods: We will compare the characteristics of patients identified with non-diabetic hyperglycaemia in GP patient records (using the National Diabetes Audit dataset, NDA) to the characteristics of patients identified with non-diabetic hyperglycaemia in representative survey data for England.

The English Longitudinal Study of Ageing (ELSA); Understanding Society and the Health Survey for England (HSE) surveys record HbA1c test results (enabling an assessment of non-diabetic hyperglycaemia) and contain comparative measures of social class (sourced via Lower Super Output Area (LSOA) IMD score with LSOA and/or IMD score obtained via special access license), ethnicity, sex, and disability status. Multivariable probability analysis will be used to test if the probability of having non- diabetic hyperglycaemia differs across surveys for particular patient characteristics. ^{66 67} This analysis will identify whether patients identified as non-diabetic hyperglycemic in primary care records differ from those in nationally representative surveys. We will use:

- a) Understanding Society waves 2 and 3 (2010-2012). All adult respondents are surveyed but blood samples were taken of 13,107/35,937 eligible (12,162 instances of HbA1c (mmol/mol) being recorded), all ages 16 and over, 964 participants with HbA1c between 42-47 mmol/mol

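### WP 4.5 treats any mean HbA1c difference below 5 as a similar effect, which is too wide a tolerance between two active programmes, and its stated inputs give a sample size of 318, not 486

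*Protocol*

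**What the plan says.** The point concerns the Power calculation paragraph of Protocol WP 4.5, the comparison of face-to-face and digital delivery.

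- Starting values: "HbA1c at 6 months among those taking the F2F DPP is 39.9 mmol/ml (SD 4.08" (the unit is evidently a misprint for mmol/mol, which is used elsewhere).
- Threshold: "A reduction in HbA1c of 5 mmol/ml (0.5%) or more is considered to be clinically important".
- Inference drawn from it: "so if the difference in the means of the two groups is less than 5 they can be regarded as having a similar effect".
- Sample size assumptions: "Assuming a standard deviation in both F2F and digital DPP of 4.08, 90% power, alpha 5% and 5-to-1 allocation of controls to cases".
- Result: "to observe a difference of 2 mmol/ml we would need a total of 486 people (81 digital, 405 F2F".
- Availability: "There are 2200 digital participants with 6 month outcomes, which should provide sufficient numbers, after matching".

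The Analysis section of WP 4.5 specifies random effects linear regression for weight and HbA1c, with 1:5 nearest neighbour matching. It does not return to the value 5, and it sets no other margin or confidence-interval rule for similarity. The Missing data section limits the effectiveness analysis to completers.

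**The concern.** The paragraph has two separate faults.

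**The criterion for similarity.** A reduction of 5 is described as clinically important. It does not follow that two active programmes differing by just under 5 have a similar effect. One of them could fall short of the other by nearly a whole clinically important reduction and still meet the description. The comparison uses the difference in means alone, so precision plays no part. It also conflicts with the next sentence, which treats a difference of 2 as worth detecting with 90% power. A difference of 3, say, would be both something the study is built to find and something it may call similar.

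**The sample size.** The stated inputs do not lead to the stated total.

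At stake is how the result of WP 4.5 objective 3 (clinical effectiveness among completers) is worded. A statement that the two delivery modes have a similar effect would say little if it rested on this tolerance.

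**Working it through.** **1. The stated sample size.** Inputs, all from the Power calculation paragraph: difference 2, SD 4.08 in both groups, power 90%, alpha 5% (sidedness not stated, taken as two-sided), five face-to-face to one digital.

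n(digital) = (1.960 + 1.2816)² × 4.08² × (1 + 1/5) / 2² = 10.508 × 16.646 × 1.2 / 4 = 52.5, rounded up to 53.

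Face-to-face = 5 × 53 = 265. Total = **318**, against 486 stated. An exact t-test calculation also gives 318.

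Power at the stated size: SE = 4.08 × √(1/81 + 1/405) = 0.497. Then 2/0.497 − 1.96 = 2.07, which is a power of about **98%**, not 90%.

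Attempts to recover 486:

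| Variant | Total |
|---|---|
| One-sided 5%, 90% power | 258 |
| Two-sided 5%, 95% power | 390 |
| Two-sided 1%, 90% power | 450 |
| One-sided 5%, 99% power | 474 |
| Equal allocation, two-sided 5%, 90% power | 176 |

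None matches with the stated settings. An SD of about 5.07 would do so: 2 / (3.2416 × 0.1217) = 5.07. An allowance for about 35% loss comes close: 53/0.65 = 81.5, so 82 digital. The paragraph states neither.

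**2. How wide 5 is.** 5/4.08 = 1.23 SD. It is 2.5 times the difference of 2 used for sizing. It also equals the span of the HbA1c range for non-diabetic hyperglycaemia (WP 1.1 Methods: "964 participants with HbA1c between 42-47 mmol/mol").

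**3. What 5 allows, over the possible baselines.** The protocol does not give the mean baseline HbA1c of participants. I assume it lies within 42–47, that it is equal in both groups, and that the digital arm does not change at all. The 6-month difference then equals the face-to-face fall to 39.9.

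| Assumed mean baseline | Fall to 39.9 = difference | Below 5? |
|---|---|---|
| 42 | 2.1 | yes |
| 44.5 | 4.6 | yes |
| 44.9 | 5.0 | boundary |
| 45 | 5.1 | no |
| 47 | 7.1 | no |

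The switch is at 39.9 + 5 = 44.9. At a baseline of 47 the tolerance still allows digital to lose 5/7.1 = 70% of the face-to-face fall.

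The chance that the point estimate falls below 5 is equally sensitive. With SE 0.497 (81 + 405) it is about 79% at a true difference of 4.6 and about 42% at 5.1. With 2,200 digital matched 1:5, SE = 4.08 × √(1/2,200 + 1/11,000) = 0.095, and the chances are almost 100% and about 15%.

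**4. Conflict with the test that the size is built for.** At 81 + 405 a difference reaches two-sided significance at about 1.96 × 0.497 = 0.97. Any observed difference between about 1 and 5 would therefore be statistically significant and also similar under the stated inference. With 2,200 matched 1:5 that band starts at 1.96 × 0.095 = 0.19. Both figures ignore clustering.

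**5. Size for a similarity claim.** This takes a margin of 2 purely as an illustration, with a true difference of 0 and 90% power.

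- Two one-sided 5% tests (90% CI): (1.645 + 1.645)² × 16.646 × 1.2 / 4 = 54.1, so 55 + 275 = 330.
- 95% CI: (1.960 + 1.645)² × 16.646 × 1.2 / 4 = 64.9, so 65 + 325 = 390.

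Neither allows for clustering by provider or CCG, which the analysis models.

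**The case against.** The strongest reply is that 5 is not an operative decision rule. It appears once, as rationale in a power paragraph. The Analysis section estimates adjusted differences by regression and never refers back to it. A true difference as large as 4.6 would be detected almost with certainty by the test that the paragraph sizes for. This stands in part: the estimate itself is not damaged, only what may be said about it. But the sentence is the only criterion for similarity in WP 4.5, and nothing in the analysis text replaces it.

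A reader might go further and infer that the plan would pass a digital programme with no effect. The protocol does not support that as a general statement. It depends on a baseline mean that is not given: it is true below about 44.9 and false above it, and both lie within 42–47. The population does not settle the matter. The pilot registered "3612 with NDH and 797 who were obese", so about 18% (797/4,409) of digital registrants were outside the non-diabetic hyperglycaemia group. That makes equal baselines a further assumption.

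A reader might also infer that the wrong total leaves the comparison underpowered. It does not: 486 exceeds 318, and the outcome data already exist.

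Nor does the protocol make any decision about offering patients a choice depend on WP 4.5. The section on the digital programme ties that possibility to release of the pilot results and describes a separate embedded evaluation. WP 4.5 is a secondary, completers-only observational analysis, and its Missing data section itself warns of systematic bias.

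**Conclusion.** Both faults are in the protocol as written, and their weight is moderate.

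The inference from 5 is invalid whatever the baseline. It reuses an important reduction as a tolerance between active programmes, ignores uncertainty, and contradicts the difference of 2 in the next sentence. How lax it is depends on the unstated baseline. With equal baselines and an unchanged digital arm, similarity would be met below about 44.9. At the top of the range, a loss of about 70% of the face-to-face fall would still pass.

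The sample size should read 318 on the stated inputs (two-sided). The excess of 168 (53%) is either an error or an unstated allowance. It is conservative and does not threaten the adequacy of the 2,200 digital participants.

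**What to change.** 1. Delete the inference that a difference in means below 5 indicates a similar effect.
2. Report the adjusted difference in HbA1c with its 95% CI. Claim similarity only if that interval lies wholly within a pre-stated margin. The margin should be clearly smaller than 5 and justified against the face-to-face change from baseline, which the team can state because it already holds the face-to-face dataset.
3. The plan's own 2 is a candidate margin, but it was chosen as a detectable difference and needs its own justification. It would need about 330 to 390 people in total, depending on the confidence level, before any allowance for provider and CCG clustering.
4. Restate the size for detecting 2 as 318 (53 digital, 265 face-to-face), or state the inflation or inputs that produced 486. State that alpha is two-sided, and correct the unit to mmol/mol.

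The cost is wording only, since no new data are needed. The downside is that similarity becomes harder to claim.
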